7.5 Subgroup analyses

We will perform subgroup analyses for the primary outcome by gestational age category (≤ 26 weeks; > 26 weeks) and growth centile ($< 10\%$ centile; $\geq 10\%$ centile). The subgroups will be examined through use of an interaction term between the subgroup and the intervention arm. Results will be judged at an alpha of 0.20, presented as forest plots, and will be hypothesis generating.

7.6 Exploratory analyses

Exploratory analyses will be undertaken to estimate how the volume of supplementary feed (pHDM or formula) and the time of introduction impacts outcome. This will be performed using Parametric G-formula, a method to estimate the effects of treatment strategies adjusting for time-varying confounders affected by prior exposures.

7.7 Safety analyses

We will tabulate adverse events by intervention arms for each randomisation. For safety events of special interest (death, surgical NEC, medical NEC, infection) we will follow the principle of the primary analysis. For all other events we will calculate the incidence rate ratio and present these graphically using dot plots.

7.8 Mechanistic sub-study

We will prepare a mechanistic Statistical Analysis Plan prior to any data analyses. We will use Tract-based Spatial Statistics (TBSS) optimised for neonates to compare voxel-wise statistics

Title: COLLABORATE	EDGE No: 181495	Sponsor: Imperial College London	Version: 3.0; 09/01/2026
---------------------------	---------------------------	--	---------------------------------

across the white matter skeleton between treatment groups using a general linear model adjusting for gestational age at birth, age at image acquisition, and any important covariates that remain imbalanced after randomisation (35,36). Significance will be set as $p < 0.05$, following family-wise error rate correction and threshold-free cluster enhancement. TBSS results will be reported as maps overlaying the skeleton where voxels with p -values < 0.05 are highlighted using a colour bar to show the range of significant values.

Participants will be excluded from TBSS analyses if i) there is a parenchymal injury or brain abnormality identified on structural MRI by clinical reviewers considered likely to confound image registration; ii) if there is no diffusion MRI, or excessive motion; iii) if more than 10 diffusion weighted MRI volumes had slice dropout; or iv) if registration fails. Application of these exclusion criteria will be blind to treatment group allocation to reduce the risk of selection bias. Image analysts will be blind to treatment group allocation until analyses are completed.

Diffusion tensor imaging (DTI) data will be analysed using Functional MRI of the Brain Software Library (37) and DTI-ToolKit. Data will be corrected for phase encoding distortions, eddy-induced distortions and motion using the topup-eddy algorithm, using T2 structural volumes rigidly registered to b0 maps and assuming a bandwidth of zero (no phase-encoding) (38). A diffusion tensor model will be fitted to each voxel and the eigenvalues and eigenvectors used to convert the corrected diffusion weighted images into diffusion tensor volumes.

Tensor-based image registration will be used to produce a population-specific diffusion tensor template. From this template the mean Fractional Anisotropy (FA) volume is derived and thinned by perpendicular non-maximum suppression to create the mean white matter tract skeleton, thresholded at $FA > 0.15$ to exclude peripheral tracts. All participants' diffusion tensor volumes will be registered to the diffusion tensor template and FA and other parameters extracted and projected onto the white matter tract skeleton.

7.9 Cost effectiveness study analyses

As COLLABORATE will be viewed as providing definitive evidence by the medical community, there is a pressing need to establish the value for money of pHDM versus preterm formula, especially due to the large cost difference between the two interventions and the high costs of NEC treatment (39). NHS secondary care utilisation from randomisation until neonatal unit discharge will be obtained from the NNRD, as used in other successful economic evaluations (40, 41).

To calculate the costs associated with daily neonatal care received by each baby, we will multiply the number of days spent receiving each level of care, by level-specific national average bed day costs sourced from National Schedule of NHS Costs (42). Such costs are estimated by assigning each level of care a healthcare resource group (HRG) code. HRG are groupings of clinically meaningful activities made primarily on the basis of diagnosis and procedure codes, and within the NHS, are the 'units' of healthcare for which providers receive payment. Costs assigned to each HRG are based on nationally estimated reference costs developed into adequately cover the cost of providing high-quality and cost-effective care. For this analysis, the neonatal bed day costs use will be intensive care (HRG XA01Z), high dependency care (HRG XA 02Z), special care without carer resident alongside baby (HRG XA03Z), special care with carer resident alongside baby (HRG XA04Z) and normal care (HRG XA05Z).

Given that some major clinical activities are not included in these neonatal care HRG we will identify high-cost non-routine procedures captured within the NNRD, considered to be important in this particular population. For example, types of neonatal surgery will be identified from their corresponding Operating Procedure Code Standard and International Statistical Classification of Diseases and Health Related Problems (ICD-10) codes for costing purposes and unit costs obtained from the NHS National Schedule of Costs.

Title: COLLABORATE	EDGE No: 181495	Sponsor: Imperial College London	Version: 3.0; 09/01/2026
---------------------------	---------------------------	--	---------------------------------

For both trial comparisons, cost results will be reported as means with standard deviations. Mean differences, together with 95% confidence intervals, will be estimated using multilevel generalised gamma linear models with a random intercept at the neonatal unit level. For comparison 2 (fortification versus no fortification), results will additionally be presented by subgroup: no clinical need for supplementation of mother’s own milk; and if supplementation is required, by randomisation group in comparison 1, i.e. pHDM and Preterm Formula. Costs will be presented alongside the key primary and secondary outcomes by intervention arm in both comparisons with associated uncertainty. We will use the NNRD to determine the number of extremely preterm babies and hence estimate the NHS budget implications for the UK of all study interventions. This approach will enable various stakeholders (e.g. parents, clinicians and commissioners) to contemplate the impact of pHDM and milk fortification on the outcomes of most relevance to them.

If trial interventions result in better 2-year cognitive-language outcomes, we will develop a decision analytical model to estimate the cost-effectiveness of the intervention up to 18 years of age. This analysis will be conducted from an NHS and societal perspective and the main outcome measure in the economic evaluation will be the child’s quality-adjusted life years (QALY). A Markov model will be constructed representing the natural history of infants to extrapolate the within-trial cost-effectiveness results using annual cycles. The structure of the model will be established and agreed within the research team. Observed outcomes and health care resource utilisation for randomised infants will be used to inform the characteristics of a hypothetical cohort entering the model. Transition probabilities indicating movement across health states during the first two years will be obtained from the trial, whereas transition probabilities after the second year will be informed through literature searches. Health care costs and health-related quality of life estimates incurred annually in each health state after neonatal care discharge will be obtained from the literature. Data on informal care and impact on productivity of parents to inform cost parameters in the model will also be obtained from the literature if available.

To be able to follow-up trial participants using routine sources, we will seek parent consent to access long-term data. This will enable future data linkage to the Department for Education National Pupil Database on performance in Key Stage 1 and Special Educational Needs, and use of health services and mortality through Hospital Episode Statistics.

7.10 Internal pilot

We will run an internal pilot to assess recruitment rate; co- enrolment rate; and withdrawal of consent rate. The internal pilot will run for 9 months (6-15 months).

We need adequate recruitment for each of the comparisons to be powered to detect the MCID of 0.05. We estimate recruitment will increase over the first 9 months from 25 per month to an average of 97 by month 6.

The proportions of babies taking part in both randomisations is important to monitor as this will impact the power of the study. If less than 30% take part in both randomisations, then power will be <80%.

We will also monitor the sample size assumption for missing data which will occur when carers/parents withdraw consent for use of their baby’s information in NNRD to be analysed.

The internal pilot will run seamlessly into the main study if all three criteria below are met.

Progression Criteria	Recruitment per comparison	Proportion taking part in both trials	Withdrawn consent for use of NNRD data
-----------------------------	-----------------------------------	--	---

Title: COLLABORATE	EDGE No: 181495	Sponsor: Imperial College London	Version: 3.0; 09/01/2026
---------------------------	---------------------------	--	---------------------------------

RED: Consider Stopping	<322 randomisations in each comparison	<30% (as trial will have <80% power)	>10%
AMBER: Explore approaches to achieve target	322-644 randomisations in each comparison	30-50%	>2% but < 10%
GREEN: Continue without changes	>644 recruited to each comparison	>50%	<= 2%

The Trial Steering Committee will be responsible for assessing the internal pilot outcomes and provide guidance to the trial team.

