7.2 Sample size and power

7.2.1 Main study

This is a group-sequential trial with 2 interim and 1 final analysis (i.e., an adaptive trial), hence the sample size is not fixed. The maximum sample size is 3252, (n=2168 in each randomisation; n=1084 per arm) assuming no early stopping, estimated on the composite primary efficacy outcome (survival to 34 weeks gestational age without surgical NEC (Y/N)).

Title: COLLABORATE	EDGE No: 181495	Sponsor: Imperial College London	Version: 3.0; 09/01/2026
---------------------------	---------------------------	--	---------------------------------

For the randomisation 1 (pHDM vs Formula supplement) an observational analysis of NNRD data estimated the difference in the proportion surviving to 34w PMA for babies born <29 weeks' gestation to vary between 0.18 and 0.52 depending on week of gestational age (favouring supplementation with preterm formula) (6) For the sample size calculation we targeted a highly conservative MCID in this proportion of 0.05 based on a baseline of 0.82 which we accurately estimated from the NNRD for this population of babies in the UK (i.e. from 0.82 to 0.87).

For randomisation, 2 (fortifier vs no routine fortifier) an unpublished observational analysis from NNRD data estimated the difference in proportion data surviving to 34w PMA for babies born <29 weeks gestation to vary between 0.06 and 0.75 depending on week of gestational age (favouring fortifier). Taking a conservative approach and in line with the first comparison, we have chosen to target the same MCID of 0.05.

We have calculated power based on a fixed sample size of 3252 unique babies using rpact (33) where interim timings were chosen to minimise the expected sample size. We anticipate at least 50% of babies will be co-enrolled into both randomisations. If co-enrolment is higher, power will increase. We have used an O'Brien & Fleming design with two-sided overall significance level of 5% to account for two interims at 50% and 75% and a normal approximation assumption for rates. For both randomisations we have factored in 2% missing outcome data due to carers withdrawing consent from routine data collection in NNRD.

Based on all the above assumptions, n=3252 (n=2168 in each randomisation and n= 1084 per arm) will achieve a minimum of 87% power for each randomisation. The expected sample size across for each randomisation is n=2439.

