7.4 Interim assessment of efficacy

We will conduct two pre-planned formal interim efficacy analyses when 50% and 75% of participants reach 34 weeks gestational age (i.e., primary outcome is available). This analysis will be undertaken by an independent ICTU statistician. Recruitment will continue during interim analyses. The analysis will employ two-sided O'Brien-Fleming efficacy boundaries. Unadjusted between arm differences in proportions will be calculated using the primary analysis models described for the final analysis. An identify link function will be used to obtain adjusted risk differences and corresponding Z-scores. Superiority will be assessed at each stage based on the critical value thresholds (Z-scores) and numbers of participants.

Proportion recruited	50%	75%	100%
Randomisation 1, n	954	1431	1908
Randomisation 2, n	1063	1594	2126
Critical value thresholds (Z-scale)	2.863	2.337	2.024

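### The reason given for the 30% co-enrolment limit (power below 80%) conflicts with section 7.2.1: with its 2% loss, power at 30% is about 84%

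*Protocol*

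**What the plan says.** Section 7.2.1 sets the design. It holds the number of babies fixed: "We have calculated power based on a fixed sample size of 3252 unique babies using rpact". The target is a five-point difference ("i.e. from 0.82 to 0.87"), tested with an "O'Brien & Fleming design with two-sided overall significance level of 5% to account for two interims at 50% and 75" per cent. On overlap it says "We anticipate at least 50% of babies will be co-enrolled into both randomisations". It allows for 2% missing outcomes in both randomisations and concludes that "n=3252 (n=2168 in each randomisation and n= 1084 per arm) will achieve a minimum of 87% power for each randomisation".

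Section 7.4 gives the stopping limits ("Critical value thresholds (Z-scale) 2.863 2.337 2.024") and the numbers for analysis at 100% recruitment: 1908 for randomisation 1 and 2126 for randomisation 2.

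Section 7.10 makes co-enrolment one of three pilot progression criteria. The text says "If less than 30% take part in both randomisations, then power will be <80" per cent, and the RED row of the table repeats the reason: "<30% (as trial will have <80% power"). AMBER is 30 to 50% and GREEN is above 50%. Section 7.11 says that meeting a red criterion leads to a discussion with the Trial Steering Committee about stopping.

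**The concern.** The RED limit is justified by a power figure, so that figure should follow from the design assumptions. On the 2% loss in section 7.2.1, a trial at 30% co-enrolment appears to be well above 80% power. The section 7.4 table implies a different loss for randomisation 1 and gives no reason for it. Section 7.10 does not say which randomisation its statement concerns, or what the 30% is a share of. The Trial Steering Committee would be asked to discuss stopping on a stated reason that it could not reproduce from the sample size section, and two members could calculate the criterion differently from the same data.

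**Working it through.** **Inputs.** Rates 0.82 and 0.87, 3252 unique babies, 2168 per randomisation (1084 per arm), 50% co-enrolment and 2% loss: section 7.2.1. Limits 2.863, 2.337 and 2.024 at 50%, 75% and 100%, and final numbers 1908 and 2126: section 7.4. RED limit 30%: section 7.10.

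**Power formula.** With n analysed per arm, the expected final Z is 0.05 / √[(0.82×0.18 + 0.87×0.13)/n] = 0.05 / √(0.2607/n). Power is the probability that |Z| crosses its limit at any of the three looks (trivariate normal, correlations from information 0.5, 0.75 and 1). With no difference between arms, the three limits give a two-sided error of 0.050, as stated.

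**Reproducing the plan.** 1084 × 0.98 ≈ 1062 per arm; expected Z = 3.19; power 88.4%. This agrees with the stated minimum of 87%.

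**What co-enrolment is a share of.** The planned overlap is 2 × 2168 − 3252 = 1084 babies.
- Share of each randomisation: 1084/2168 = 50%, which matches the plan. The size of each randomisation is then 3252/(2 − c).
- Share of unique babies: 1084/3252 = 33%. On this reading 50% would give 3252 × 1.5/2 = 2439 per randomisation, not 2168.

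The first reading is used below.

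**At 30% with the 2% loss of section 7.2.1.** 3252/1.7 = 1913 per randomisation; × 0.98 / 2 = 937 per arm; expected Z = 3.00; power 84.2%.

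**Where power reaches 80%.** This needs about 838 analysed per arm, or 1676 in all. With 2% loss, 1676/0.98 = 1710 must be randomised, so c = 2 − 3252/1710 ≈ 10%.

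**The loss implied by section 7.4.** Randomisation 1: 1908/2168 = 0.88, a 12% loss. Randomisation 2: 2126/2168 = 0.98, a 2% loss.

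| Case | Analysed per arm | Power |
|---|---|---|
| Randomisation 1 on plan, 12% loss | 954 | 84.9% |
| Randomisation 2 on plan, 2% loss | 1063 | 88.5% |
| Randomisation 1 at 30%, 12% loss | 842 | 80.2% |
| Either randomisation at 30%, 2% loss | 937 | 84.2% |

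With 12% loss the 80% point needs 1676/0.88 ≈ 1904 randomised, so c = 2 − 3252/1904 ≈ 29%. This is close to the protocol's 30%.

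**The case against.** The strongest defence is that section 7.4 is as much part of the plan as section 7.2.1. It expects 1908 analysed in randomisation 1. With that fraction, power at 30% is 80.2% and the 80% point is about 29%. A statement about the power of the trial may reasonably refer to its weaker comparison, and on that basis the limit is right to within a percentage point. This stands. A reader might infer that the RED rule is a false trigger that would send an adequately powered trial to a stopping discussion; for randomisation 1 the documents do not support that. The defence does not rescue the text as written, however. The 12% is nowhere stated, it contradicts the 2% given for both randomisations, and it contradicts the 87% minimum for each.

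A reader might also take 30% as a share of unique babies, which gives 3252 × 1.3/2 = 2114 per randomisation and about 88% power. That reading does not reproduce 2168 at 50%. Its figure of 2439 does appear in section 7.2.1, but as an expected sample size and not as the number behind the power statement. Nor does the GREEN limit need to change: 1084/2168 already puts the planned overlap at 50%.

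Two further points are fair. The calculation assumes that the two randomisations stay equal in size as overlap falls; if they did not, the smaller would have less power. And RED prompts a discussion with a committee that includes an independent statistician, so nothing stops automatically.

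**Conclusion.** The concern holds as an inconsistency between sections 7.2.1, 7.4 and 7.10. On the 2% loss stated for both randomisations, power at 30% co-enrolment is about 84%, and it drops below 80% only under about 10%. For randomisation 2 the statement in section 7.10 is wrong on either section's numbers (about 84% at 30%). For randomisation 1 it is approximately right, but only with a 12% loss that the text does not explain and that lowers its planned power to about 85%, against a stated minimum of 87%. Sections 7.2.1 and 7.10 therefore cannot both be correct.

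These figures rest on 3252 unique babies, equal-sized randomisations, 0.82 against 0.87, the limits in section 7.4, and co-enrolment as a share of each randomisation. That the 30% limit was derived from the 12% loss is an inference from the arithmetic; the protocol does not say so.

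**What to change.** 1. Reconcile the loss for randomisation 1: either 2% as in section 7.2.1 or the 12% implied by 1908 in section 7.4. If 12% is intended, give the reason.
2. State in section 7.10 that co-enrolment is measured as a share of each randomisation. As a share of unique babies the planned overlap is 33%, so a trial exactly on plan would be rated AMBER and lie close to RED.
3. Correct the RED rationale to match:
   - If 2% holds for both, replace the claim of less than 80% power with about 84% at 30%, and note that the 80% point is about 10%. The 30% limit can be kept as an operational trigger if wanted.
   - If 12% holds for randomisation 1, confine the claim to randomisation 1 and restate its planned power in section 7.2.1 as about 85%.

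The cost is an edit to the text and progression table of section 7.10 and to section 7.2.1 or 7.4. No extra babies are needed.

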7.11 Early discontinuation of the study

The study may be prematurely terminated for the following reasons:

- Event/s which in the opinion of the Data Monitoring and Ethics Committee contraindicate/s randomisation of additional participants
- Sponsor decision
- Research ethics committee decision
- Funder decision

An internal pilot will take place for the first 9 months after recruitment starts. It will use traffic light system: if the red criteria are met there will be a discussion with the Trial Steering Committee about stopping the trial.

The Data Monitoring and Ethics Committee Charter will define procedures for early termination of the study due to safety or efficacy, should this be required. As this is a comparative-effective trial embedded in standard care, in the case of early discontinuation, all procedures will continue except the mechanistic sub-study.

8 REGULATORY, ETHICAL AND LEGAL ISSUES

8.1 Declaration of Helsinki

The investigators will ensure that this study is conducted in full conformity with the 2024 revision of the 1964 Declaration of Helsinki.

8.2 Good Clinical Practice

The study will be conducted in accordance with the guidelines laid down by the International Conference on Harmonisation for Good Clinical Practice (ICH GCP E6 guidelines).

8.3 Research Ethics Committee Approval

8.3.1 Initial approval

Prior to the enrolment of participants, the Research Ethics Committee (REC) must provide written approval for the conduct of the study at named sites, the protocol and any amendments, the Participant Information Sheet and Consent Form, any other written information that will be provided

Title: COLLABORATE	EDGE No: 181495	Sponsor: Imperial College London	Version: 3.0; 09/01/2026
---------------------------	---------------------------	--	---------------------------------

to the participants, any advertisements that will be used and details of any participant compensation.

8.3.2 Approval of amendments

Proposed amendments to the protocol and aforementioned documents will be submitted to the REC for approval. Amendments may be implemented only after a copy of the REC approval letter has been obtained.

Amendments that are intended to eliminate an apparent immediate hazard to participants may be implemented prior to receiving Sponsor or REC approval. However, in this case, approval must be obtained as soon as possible after implementation.

The Trial Management Group will make the decision to amend the protocol and decide whether changes are substantial or non-substantial with support from the Trial Steering Committee, and Data Monitoring and Ethics Committee and advice from the Parent, Patient and Public Involvement and Engagement Advisory Group if applicable.

Changes will be communicated to stakeholders, including participating sites, electronically and version controlled with tracked changes and in accordance with relevant standard operating procedures. The amended protocol will be reviewed by all members of the Protocol Development Group and funder prior to finalising.

